1b) Is fatal HIV-TB associated with translocation of bacteria and their products from the intestine into blood?

Under this aim, the first hypothesis is that in patients with severe HIV-TB, intestinal translocation of bacterial products (LPS and bacterial DNA) will be higher than in control HIV-infected patients with similar CD4 counts who do not have TB. The second hypothesis is that mortality will be associated with higher levels of bacterial product translocation. Thirdly we hypothesise that translocation of viable intestinal bacteria in some patients results in life-threatening deterioration and death.

To test the first 2 hypotheses the following will be performed:

- i) Plasma LPS concentration using Chromogenic Limulus Amebocyte Lysate test [17];
- ii) Plasma soluble CD14 (secreted by macrophages/monocytes in response to LPS) by ELISA [17, 34];

- iii) Plasma intestinal fatty acid binding protein (I-FABP; a marker of small intestine mucosal damage) [35-38] by ELISA;
- iv) Whole blood bacterial DNA concentrations will be measured using Abbott PLEX-ID platform [39-41]. Specimens will be shipped to Abbott Laboratory (Carlsbad, CA, US). Steps are: DNA extraction (using reagents prepared to minimise bacterial contamination), PCR amplification of bacterial DNA using broad-range, unbiased primers targeted at conserved regions of bacterial genomes, then electrospray ionization/mass spectroscopy. Amplicons are identified by ESI/MS based on recognisable patterns of base composition for different bacterial species. Quantification is performed by comparison with an internal calibrant. Similar approaches were used to study translocation in liver disease [15, 16] and inflammatory bowel disease [42].

We will perform LPS, sCD14 and I-FABP in all 660 participants and compare with the non-TB control group (n=90). For the PLEX-ID we will perform 270 PLEX-ID assays in a nested case-control study (90 fatal cases, 90 survivors and 90 non-TB controls). For all experiments comparisons will be made between fatal cases and survivors using multiple linear regression to adjust for covariates (eg. CD4 count, antibiotic treatment).

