Bacterial sepsis is characterized by an early phase of pro-inflammatory “cytokine storm”. It is now recognized that this is followed by a phase characterized by monocyte deactivation, impaired neutrophil function, lymphocyte dysfunction and apoptosis [51, 52], increased production of IL-10 and TGF- β [53] and increased proportion of circulating T-regulatory cells [54]. This “immunosuppressive phase” results in a heightened risk for secondary bacterial infections [51, 55]. We will explore whether severe HIV-TB, through similar mechanisms, results in an immunosuppressive state (prior to ART) that exacerbates HIV-related immunosuppression and may predispose to bacterial infections. Specifically, we will explore whether severe HIV-TB and mortality are associated with:

- i) Immune activation-induced apoptosis;
- ii) Increased programmed death-1 (PD-1) signaling;
- iii) Anti-inflammatory cytokine profile.

Experiments will be performed on samples from:

- 290 patients in the cohort sampled consecutively provided FACS can be performed the same day (estimated mortality of 15% will result in 44 fatal cases and 246 survivors);
- Non-TB control group (n=30).

i) Immune-activation induced apoptosis

We hypothesise that severe HIV-TB induces apoptosis of immune cells and that this is associated with mortality. PBMC will be separated and same day FACS analysis for surface markers of cell activation (CD38, HLA-DR) and a marker of apoptosis (Annexin-V) on CD4 and CD8 T-lymphocytes and monocytes will be performed on a BD LSR Fortessa instrument at the IDM. Data will be analysed using FlowJo software (TreeStar Inc, FlowJo Africa scheme).

ii) PD-1 signaling pathway

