660 patients will be enrolled. Assuming 5% loss to follow up, 630 patients will complete the study. We will exclude from major analyses patients diagnosed with rifampicin resistance (estimated 5% [77], n=30), leaving 600 for analysis. This will allow us to detect statistical significance for a two-fold difference in urinary LAM, a 15% difference in plasma LPS and a difference in the percentage of patients with detectable CMV viraemia of 20% in survivors and 40% in those with fatal outcome (or 10% and 30% respectively).

Sample size for FACS experiments (44 fatal cases vs 246 survivors) was based on Annexin-V experiments, allowing us to detect a significant difference in the proportion of CD4 T-lymphocytes that are Annexin-V+ of 5% in survivors and 20% in those who die (alpha=0.05, beta=0.2).

Characteristics of the study population:

Number of participants:

660 participants with HIV-TB co-infection.

Inclusion criteria:

1. Microbiological diagnosis of TB, or clinical diagnosis that fulfills WHO criteria for smear-negative or extrapulmonary TB [78] or suspected to have active TB based on clinical presentation
2. 18 years or older
3. Informed consent from patient (unless drowsy/confused – see below)
4. HIV seropositive
5. CD4 count \leq 350cells/ μ l

Exclusion criteria:

1. HIV seronegative or testing declined
2. Pregnant
3. 3 or more doses of TB treatment received during the admission or has been on TB treatment within one month of admission

TB case definitions:

TB will be investigated with 2 sputa for Xpert MTB/RIF and TB culture, Myco/F Lytic blood culture, urinary lipoarabinomannan (LAM) and samples from appropriate extrapulmonary sites for TB culture. Chest radiographs will be performed in all and abdominal ultrasound at clinician discretion. We will stratify analyses according to:

- 1) Confirmed TB: Microbiologically proven TB (by culture or Xpert MTB/RIF, or post-mortem findings of AFB+ or culture+) (predicted to be > 70% based on previous study at our hospital [79])
- 2) Probable TB: TB not confirmed, but urinary LAM+ or fulfill WHO criteria [78] unless an alternate diagnosis is made during follow-up or post-mortem.

Vulnerability:

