Patients who are admitted with HIV-TB co-infection (or suspected co-infection) may be confused or drowsy at time of hospital admission due to neurological TB or a general medical condition. Effort will be made to include patients who are confused or drowsy, yet eligible for the study, in order to make results generalizable to these patients.

In previous discussion with UCT HREC (in relation to a similar observational cohort study that was performed at Madwaleni Hospital, HREC REF 136/2011) regarding consent for drowsy or confused patients we were made aware that relatives or next of kin may not legally provide consent for participation in research. However, in situations where the exclusion of such patients would compromise the generalizability of the results and the risks involved in participation are minimal, such patients may be enrolled with the permission of the Ethics Committee in each case. In this study it is critically important that we obtain data on the most severely ill patients to avoid our results being biased. We thus seek Ethics Committee permission to enroll such patients (confused or

drowsy patients who fulfill inclusion criteria but are unable to provide consent to the study). If family members are present we will explain our actions to the closest adult relatives. We will not ask them to sign informed consent, but if they request us for any reason to not enroll the patient, we will respect their wishes. When such patients regain the capacity to provide informed consent, the study will be discussed with them. If they choose to participate then they will sign informed consent. If they decline to participate then their study data and sample will be destroyed. If the patient does not regain the cognitive ability to consent, specific permission will be sought from the UCT HREC to use that patient's data and sample for the study in each case. We seek permission to use this approach for enrolment for the main study and for the PK sub study (specifically for the group who are receiving medication via a nasogastric tube in the PK sub study). We will not enroll any patients who are unable to consent for genetic testing or as control patients.

HIV testing:

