Relatives will be approached for permission for post-mortem examinations. If unwilling to have a full post-mortem performed, permission will be sought to undertake post-mortem needle biopsies of lung, liver and spleen and bone marrow – an approach that yields important diagnostic information in HIV-infected patients [14, 81]. Tests performed on tissue samples will include: histological stains; Gram, fungal and ZN stains; immunohistochemical staining (CMV); and bacterial, TB and fungal cultures. This study will be performed in collaboration with [name] (Anatomical Pathology, UCT).

Study Outline of Activities:

	D0	D3	Wk2	Wk4	Wk8	Wk12	Deterioration
Informed consent	x						
Clinical Assessment	x	x				x	x
Samples Collected	x	* PK					#x
^Δ ART initiation CD4 ≤ 50			x				
^Δ ART initiation CD4 >50			x				

D: Day

Wk: Week

ART: Antiretroviral Therapy

PK: PK substudy in a subset of participants

* PK samples will be stored and run in batches retrospectively.

Samples taken at time of deterioration will not be research samples, but standard of care samples appropriate to investigate the patients' condition at that time point.

^Δ If patient is not on ART at time of recruitment

Detailed Study Procedures:

Study procedure	Time Point	Detail	Volume	Standard of care or research
Clinical Assessment	All time points	Examine for features of sepsis syndrome and TB IRIS	NA	Standard of care
	D0	* Pan ophthalmic fundoscopy for features of CMV retinitis	NA	Research
Echocardiography	D0 & Deterioration	* Assess left ventricular function	NA	Research
Blood tests	D0 & Deterioration	Chemistry: * Glucose	2 ml	Standard of care
		* Lactate		Research
		* D-dimer	5 ml	Research
		* Pro-calcitonin	1 ml	Research
		* Venous blood gas	1 ml	Research
		* Liver function tests	5 ml	Standard of care
		* Renal function tests		Standard of care
		* CRP		Standard of care
		Haematology: * Full blood count and differential	4 ml	Standard of care
		Plasma: LPS concentration	2 ml	Research
		Soluble CD14	1 ml	Research
		Intestinal fatty acid binding protein	1 ml	Research
		Microbiology: * Bacterial blood culture	8 ml	Standard of care
		* Mycobacterial blood culture	5 ml	Research
		* Serum cryptococcal antigen lateral flow assay	0.5 ml	Research
		Virology: CMV viral load	2 ml	Research
		* HIV viral load	2 ml	Research
		Immunology: PBMC	10 ml	Research
		* CD 4 count	2 ml	Standard of care
		Genetic: DNA	2 ml	Research
Luminex and ELISA for cytokines	Plasma from PBMC sample	Research		

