PLEX-ID assay for bacterial DNA	3ml	Research		
Urine	D0 & Deterioration	Urinary LAM assays	20 ml	Research
Sputum	D0 & Deterioration	* Gene Xpert MTB/RIF and TB culture	NA	Standard of Care
Chest Xray	D0 & Deterioration	* Evaluate for any abnormality	NA	Standard of care
Sputum bacterial cultures	D0 & Deterioration	* All patients with infiltrate on CXR	NA	Research
Bacterial cultures on other samples	D0 & Deterioration	* Pus, urine or other samples as appropriate	NA	Standard of care
Post mortem examination	Death	If family consents to post mortem	NA	Research

D: Day

Wk: Week

NA: Not applicable

* These tests will be performed in real time and results will be made available to managing doctors as soon as the lab result is available.

Note: If any of these samples have been taken by hospital staff within 2 days of enrollment they will not be repeated but the results from the hospital sample will be used.

Consent will specifically be taken from patients for storage of remaining plasma, serum, urine and PBMC for potential future substudies (such substudies would require specific HREC permission). In addition, we will store a sample of DNA for potential future studies of genetic polymorphisms associated with outcome in HIV-TB. Again consent will be specifically obtained for this with a separate Genetic ICF. It will be made clear to participants that sample storage is optional.

In addition, PK samples will be performed on a subset of participants as described above on day 3 of TB treatment with 4ml of blood drawn at each of the timepoints (pre-dose, 1, 2.5, 4, 6 and 8 hours after taking TB medication). Samples for PK studies will be stored and run in batches and will thus not be performed in real time. Results will not be available to attending medical teams.

Control cohort of non-TB HIV-infected patients:

We will enroll a cohort of 90 hospitalised ART-naïve HIV-infected patients with CD4 counts $\leq 350/\mu\text{l}$. We will exclude TB (2 sputum cultures and urinary LAM all negative). These will be patients admitted with other HIV-related conditions (eg. cryptococcal meningitis, pneumocystis pneumonia, Kaposi's sarcoma).

Data collection methods:

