Data quality control and assurance measures will be put in place. These will include having all clinical data capture forms being checked and signed off by one other member of the study team. Data entered on the study database will be entered by one data capturer, but will be checked by a member of the study team or by another data capturer. Any errors will be recorded and discussed at the monthly study meeting. Upon completion of the study we will ensure that 3 copies of the raw data are backed-up for long term storage: one on a UCT server, one on a remote server and one on an external hard-drive that the applicant will keep secure. These data capture, entry, management and access systems have been developed in the course of many TB-HIV and other HIV studies that we have undertaken to date.

Data analysis:

TB suspects who do not have active TB (after full clinical investigation has been completed and all results obtained) will not be included in the analysis of primary endpoints. Their data may be used in secondary analyses or as control subjects. Univariate analysis will compare those who survive 12 weeks to those with fatal outcome. Bonferroni correction for multiple comparisons will be performed where appropriate. Multivariable logistic regression modeling will be approached based on pre-specified hypotheses, articulated where possible through directed acyclic graphs. Demographic variables, CD4 count, viral load, antibiotic treatment will be explored as potential confounders in addition to hypothesis specific variables. Comparison with non-TB control patients will be performed for several of the experiments as described. Data will be analyzed using de-identified study numbers.

Description of risks and benefits:

Potential risks and discomforts: This is an observational trial and there are no study specific interventions. Collection of study samples by means of phlebotomy carries minimal risk of bruising, infection at the collection site and bleeding after phlebotomy. Phlebotomy may be uncomfortable or painful during the procedure, but this resolves as soon as the procedure has been completed. The total volume of blood drawn is ~ 55ml. This amount of blood drawn would not cause complications unless patients are severely anaemic.

Risk classification: The study as a whole carries minimal risk for participants and harm due to study participation is not anticipated.

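### Non-TB controls must be ART-naive while TB cases may already be on ART, and no stated restriction or adjustment keeps the ART effect out of the TB-versus-control comparisons

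*Protocol*

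**What the plan says.** **Controls.** The protocol section on the non-TB control cohort states: "We will enroll a cohort of 90 hospitalised ART-naïve HIV-infected patients with CD4 counts" of at most 350/µl. It adds: "These will be patients admitted with other HIV-related conditions". Under Vulnerability: "We will not enroll any patients who are unable to consent for genetic testing or as control patients".

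**TB cases.** The inclusion and exclusion criteria do not mention ART. The follow-up section speaks of starting ART in participants who are not yet on it, and of referral to start or continue ART. The footnote on ART initiation in the Study Outline of Activities reads: "If patient is not on ART at time of recruitment". Participants already on ART are therefore expected. The consent criterion is also looser than for controls: "Informed consent from patient (unless drowsy/confused" is the start of an exception that lets in patients without capacity.

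**Comparisons.** The first hypothesis of 1b is that translocation in severe HIV-TB "will be higher than in control HIV-infected patients with similar CD4 counts who do not have TB". LPS, sCD14 and I-FABP are measured in all 660 participants and compared with 90 controls. PLEX-ID uses 90 fatal cases, 90 survivors and 90 controls. Aim 1d asks whether severe HIV-TB "results in an immunosuppressive state (prior to ART") that adds to HIV-related immunosuppression. It uses 290 consecutively sampled patients (44 fatal cases and 246 survivors expected) and 30 controls.

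**Adjustment.** In 1b, covariate adjustment is described for fatal cases versus survivors. The Data analysis section lists demographic variables, CD4 count, viral load and antibiotic treatment as potential confounders, alongside hypothesis-specific variables, in the context of logistic models of death. ART is not named. On suspects found not to have TB, the same section says: "Their data may be used in secondary analyses or as control subjects".

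**The concern.** The eligibility rules fix ART status in one group and leave it open in the other. If ART changes plasma LPS, sCD14, T-cell activation, apoptosis markers or PD-1 expression, the crude difference between all TB participants and controls is the TB effect plus the share of cases on ART times the ART effect. The only comparability condition named is similar CD4 counts, and all that supports it is a shared ceiling of 350/µl.

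At stake is the first hypothesis of 1b and the control arm of 1d. If ART lowers these markers, treated cases would dilute or hide a real TB effect. If ART acts the other way on some marker, they would exaggerate it. In either case, a reader of the results could not tell which part belongs to TB.

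**Working it through.** The protocol gives no sample-size calculation for the 90 or the 30 controls, so there is no stated figure to reproduce. Three checks apply.

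**1. Is the ART effect separable?** There are three groups: controls (ART-naive), TB cases ART-naive, and TB cases on ART. Take the model

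marker = a + b·TB + c·ART.

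The control mean is a, the ART-naive TB mean is a + b, and the treated TB mean is a + b + c. Three means and three parameters make the model identifiable. The estimate of b is exactly the ART-naive TB mean minus the control mean. Without other covariates, fitting an ART term and restricting to ART-naive cases give the same TB contrast. The crude comparison of all cases with controls instead estimates b + p·c, where p is the share of cases on ART.

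**2. How large might p·c be?** The protocol gives neither p nor c, so this is illustration only. Take SD 56 pg/ml from the protocol's LPS table and a true difference of 19 pg/ml (147 − 128, its smallest row, there used for deaths versus survivors). Compare 600 cases with 90 controls, two-sided alpha 0.05. Assume p = 10 to 50% and that ART lowers LPS by 10 to 30 pg/ml.

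- Smallest bias: 0.10 × 10 = 1, so 19 appears as 18; power falls from 0.85 to 0.81.
- Largest bias: 0.50 × 30 = 15, so 19 appears as 4; power falls to 0.09.

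The sign of c is itself an assumption.

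**3. What does the ART-naive contrast cost?** With a common SD, the ratio of standard errors is

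√(1/(s·n) + 1/m) ÷ √(1/n + 1/m),

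where n is the number of cases, m the number of controls and s the ART-naive share. The shares 70, 50 and 40% are assumed. For the full-cohort assays n = 600, the number the protocol expects to analyse, and m = 90:

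- Denominator: √(1/600 + 1/90) = 0.1130.
- s = 0.7 (420 cases): 0.1162/0.1130 = 1.03.
- s = 0.5 (300 cases): 0.1202/0.1130 = 1.06.
- s = 0.4 (240 cases): 0.1236/0.1130 = 1.09.

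The same formula for each comparison:

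| Comparison | Cases vs controls | Rise in SE at 70/50/40% |
|---|---|---|
| LPS, sCD14, I-FABP | 600 vs 90 | 3/6/9% |
| FACS, all cases | 290 vs 30 | 2/5/7% |
| PLEX-ID, all cases | 180 vs 90 | 7/15/22% |
| FACS, fatal cases only | 44 vs 30 | 8/19/27% |

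Where controls are few relative to cases, they limit precision and the loss is small. Where the two groups are closer in size, it is not negligible. For LPS, power for 19 pg/ml goes from 0.85 with 600 cases to 0.81 with 300.

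**The case against.** **This is one unnamed covariate, and an SAP could supply it.** Viral load and CD4 count are measured at day 0. HIV viral load enters the linear regressions in 1d, and the confounder list leaves room for hypothesis-specific variables and causal diagrams. This has weight, and viral load partly stands in for ART. But the adjustment in 1b and in the Data analysis section is framed around death, and ART is not named. The protocol itself fixes the unequal eligibility and the comparison of all 660 participants with ART-naive controls.

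**A reader might infer that ART cannot be adjusted for because controls do not vary in it.** That does not follow. ART varies among the TB cases, so an ART term is estimable, as shown above. Analysis can remove the problem.

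**A reader might infer that the consent rule confounds TB with severity to a similar degree.** The text does not support that. The 1b hypothesis concerns severe HIV-TB, so severity is partly the exposure. Controls are also inpatients, with illnesses such as cryptococcal meningitis. The bar on controls without capacity is an ethical safeguard, and the number of cases without capacity is not given. The difference is real but secondary.

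**Two further readings go too far.** The protocol does not say that non-TB suspects re-used as controls escape the ART-naive rule; it leaves this open. The phrase about the state before ART in 1d may refer only to the baseline sample, so it does not prove that 1d was meant for ART-naive patients alone.

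**Conclusion.** The point holds for ART status. As written, the TB-versus-control comparisons in 1b (first hypothesis) and 1d mix TB with ART. Neither direction nor size can be stated from the protocol: the range of 1 to 15 pg/ml for LPS rests entirely on assumed ART shares and effects. The survivor-versus-fatal comparisons are untouched, so this concerns supporting analyses and is a worthwhile, cheap improvement rather than a threat to the main result. The cost of the remedy depends on the comparison: small for the full-cohort assays and for FACS overall, larger for PLEX-ID and for fatal FACS cases alone. Those figures assume 40 to 70% of cases ART-naive and a common SD.

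**What to change.** - For the TB-versus-control comparisons in 1b (first hypothesis) and 1d, state that the main contrast is ART-naive TB participants versus controls. Obtain it by restriction, or by a linear model with TB status, ART status at enrolment and CD4 count.
- For PLEX-ID, where cases are selected, consider choosing ART-naive cases for the control contrast so that fewer assays are lost to it. In the small FACS fatal group, the ART-term model keeps all cases in the analysis. By itself it does not recover precision, because without other covariates it gives the same contrast as restriction.
- State that any TB suspect found not to have TB and re-used as a control must meet the ART-naive rule of the control cohort.
- Keep all TB participants in the fatal-versus-survivor comparisons.
- At most, add a sensitivity analysis limited to TB participants able to consent at enrolment.

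The cost is analysis wording, plus the loss of precision tabulated above in the control comparisons only. ART status at enrolment is information the study needs anyway, because its ART initiation schedule depends on it. Recruitment need not change.

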20 patients will be enrolled monthly. When potential enrollees exceed capacity on a day then recruitment will be randomised (using simple random allocation calculator) to avoid bias. This method of selecting participants to enroll will be described in an SOP. The study counselor or study nurse will administer the informed consent document with support from the study medical officer. The informed consent document makes it clear that patients will receive the same standard of care should they decline to take part in the study and that collection and testing of genetic material is optional. In addition, they will be specifically requested to consent to storage of samples for future research and informed that this is optional. After informed consent is obtained, the study team will follow up patients for 12 weeks initially as an inpatient then as an outpatient.

Research procedures and follow up (see table below):

Cumulative mortality at 12 weeks will be ascertained. Paradoxical TB-IRIS and other causes for clinical deterioration will be ascertained during the 12 weeks. Participants not on ART will initiate ART 2-8 weeks into TB treatment (2 weeks if $CD4 \leq 50/\mu l$).

Study assessments will be at 3 days (while in hospital) and subsequently every 3 days while patient remains hospitalized. The study team will review patients at any re-hospitalisation. The team will make telephonic contact at 4 weeks after enrolment and will do a clinical review of all participants at 12 weeks after enrolment. Additional study visits will be arranged in order to determine the cause of and assist with management of clinical deterioration if necessary. We will investigate for TB drug resistance and additional diagnoses (including serum cryptococcal antigen testing [80]). Patients with drug resistance or other diagnoses will be included in the study, with these findings recorded.

At discharge from hospital patients will be referred to their local TB clinic and for continuation of their TB treatment and their local ART clinic for initiation or continuation of ART. A referral letter will be written by the KDH staff or the research staff. If at any time point there is concern that patients are not on appropriate medication, the team will contact their local clinic. They will be asked to bring their medications and TB card to the clinical review visit.

Post-mortem examinations:

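### Dedicated non-TB controls must be ART-naive but the TB cohort includes patients already on ART, so the TB-versus-control contrasts in 1b and 1d confound TB with ART status

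*Protocol*

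**What the plan says.** **Controls.** The section on the control cohort states: "We will enroll a cohort of 90 hospitalised ART-naïve HIV-infected patients with CD4 counts" no higher than 350/µl. TB is excluded by two sputum cultures and urinary LAM.

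**TB cohort.** None of the five inclusion criteria concerns ART; the HIV criterion reads only "HIV seropositive". None of the three exclusions concerns ART either. The one on prior treatment is about TB drugs: "3 or more doses of TB treatment received during the admission or has been on TB treatment within one month of admission".

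**Patients already on ART are expected.** A footnote to the Study Outline of Activities qualifies the ART rows with "If patient is not on ART at time of recruitment". The follow-up section says "Participants not on ART will initiate ART 2-8 weeks into TB treatment", and at discharge patients go to "their local ART clinic for initiation or continuation of ART".

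**Contrasts.** Section 1b: "We will perform LPS, sCD14 and I-FABP in all 660 participants and compare with the non-TB control group (n=90"). It also plans PLEX-ID assays in 90 fatal cases, 90 survivors and 90 controls. The only comparability that its first hypothesis asks for is in CD4 count. Section 1d asks whether severe HIV-TB "results in an immunosuppressive state (prior to ART) that exacerbates HIV-related immunosuppression". It samples 290 cohort patients consecutively, takes 30 controls, and compares survivors, fatal cases and controls.

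**Adjustment.** Section 1b gives CD4 count and antibiotics as example covariates, for fatal cases versus survivors. The Data analysis section lists demographics, CD4 count, viral load and antibiotics as possible confounders, plus hypothesis-specific variables, directly after the logistic regression sentence. The same section lets TB suspects found not to have TB serve as controls and sets no ART condition for them.

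**The concern.** One side of each TB-versus-control contrast is ART-free by rule and the other is a mixture. If ART affects LPS, sCD14, I-FABP, bacterial DNA, activation or apoptosis markers, the observed difference is the TB effect plus the share of TB patients on ART times the ART effect. A similar CD4 count does not remove this, because treated and untreated patients with the same count can differ in viral load, which the protocol itself treats as a possible confounder and as a correlate of the 1d markers.

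At stake are the first hypothesis of 1b (more translocation in HIV-TB than in HIV without TB) and the comparison with controls in 1d. The 1d question is also phrased for the state before ART, while its sample is taken whatever the ART status.

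**Working it through.** **1. What the plan sizes.** The protocol gives no sample size or power for any TB-versus-control contrast. Its LPS table concerns survivors versus fatal cases. The 15% row (128 v 147 pg/ml, SD 56, two-sided alpha 0.05, power 0.80, 15% mortality) reproduces as 455 + 81 = 536, the stated figure. Below, that row's SD and 19 pg/ml step are borrowed for TB versus control. This is an assumption.

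**2. Inputs.** From the protocol: 600 analysable TB patients, 90 controls, SD 56, means 147 and 128. Assumed, because the protocol gives neither: the share *g* of the TB group on ART (20% or 50%) and the relative LPS reduction *r* on ART (10% or 15%).

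**3. No ART effect.** SE = 56 × √(1/600 + 1/90) = 6.33 pg/ml. Then 19/6.33 = 3.00, and power = Φ(3.00 − 1.96) = 0.85.

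**4. With an ART effect.** Observed difference = 19 − *g* × *r* × 147.

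| *g* | *r* | Difference (pg/ml) | Difference/SE | Power |
|---|---|---|---|---|
| 20% | 10% | 16.06 | 2.54 | 0.72 |
| 50% | 10% | 11.65 | 1.84 | 0.45 |
| 20% | 15% | 14.59 | 2.30 | 0.63 |
| 50% | 15% | 7.98 | 1.26 | 0.24 |

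**5. Error without a TB effect.** The imbalance can also create a difference, in whichever direction ART acts. With 30% on ART and an ART effect of 0.5 SD, the bias is 0.3 × 0.5 = 0.15 SD = 8.4 pg/ml. The chance of p < 0.05 with no TB effect is then 0.26 for 600 v 90, and 0.12 for the 290 v 30 contrast in 1d.

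**6. Restricting the TB side to ART-naive patients.** SE = 56 × √(1/(600(1 − *g*)) + 1/90).
- *g* = 20%: 480 v 90, SE 6.43, power 0.84.
- *g* = 50%: 300 v 90, SE 6.73, power 0.81.

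The 90 controls dominate the standard error, so little is lost. For FACS against 30 controls, √(1/290 + 1/30) = 0.192 becomes √(1/145 + 1/30) = 0.201 with half on ART.

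**7. Restricting fatal versus survivor in 1d.** The plan's basis is 44 fatal cases v 246 survivors, 20% v 5%, at 80% power. With the normal approximation and a continuity correction (unrounded group sizes, same ART share in both groups):
- all 290: 0.80 to 0.81, in line with the plan;
- 20% on ART (35.2 v 196.8): 0.72;
- 50% on ART (22 v 123): 0.52.

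Restriction is therefore cheap against controls but expensive for fatal versus survivor.

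**8. PLEX-ID.** The planned 90 fatal cases equal 15% of 600, so there is no reserve. Among ART-naive patients, 90 × 0.8 = 72 or 90 × 0.5 = 45 fatal cases would remain. For all TB patients against controls, √(1/180 + 1/90) = 0.129 becomes √(1/144 + 1/90) = 0.134 or √(1/90 + 1/90) = 0.149.

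**The case against.** **Viral load is measured at baseline, enters the 1d regressions and is a listed confounder; the covariate lists are open.** This is the best reply, and adjustment for it could absorb part of an ART effect. But neither list is tied to the contrast with controls: in 1b the covariates are named for fatal cases versus survivors, and in the Data analysis section they follow the mortality model. With no treated patient in the dedicated control cohort, an ART term could be estimated only within the TB group. Adjustment would then assume that ART acts equally with and without TB.

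**Not all controls need be ART-naive.** This is correct: reused TB suspects carry no ART condition. It leaves the control definition inconsistent and does not balance the groups.

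**The reference to the state before ART is a parenthesis.** It may only separate the baseline state from TB-IRIS after ART is started. That is a fair reading, so it is not evidence of a planned restriction. It still does not describe patients already on ART.

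**Stronger readings that do not hold.** A reader might infer that the comparison would be reversed. In the 10–15% scenarios the worst case still leaves +8 pg/ml; reversal needs *g* × *r* above 19/147 = 0.13, and the largest product there is 0.5 × 0.15 = 0.075. A reader might also infer that bias towards no difference is established, but no passage says that ART lowers these markers. Nor does the imbalance reach the fatal-versus-survivor comparisons, which do not use these controls. Finally, moving all of 1d to ART-naive patients is not a free correction, as step 7 shows.

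**Conclusion.** The asymmetry is plain in the text. Followed as written, the plan confounds TB with ART status in the TB-versus-control contrasts of 1b and 1d. This should be corrected, because the protocol itself fixes who is a control, who is sampled and which groups are compared.

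The size and direction of the bias are not known. The fall in power from 0.85 to 0.63 or 0.24 rests on three assumptions: the planning SD and 19 pg/ml step carry over to TB versus control, ART lowers LPS by 15%, and 20% or 50% of the TB group are on ART. The survivor-versus-fatal comparisons, and so the primary outcome, are not affected by the choice of controls.

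**What to change.** **In sections 1b, 1d and Data analysis,** state that:
- the main TB-versus-control comparisons use only TB participants who are ART-naive at enrolment, with participants on ART shown separately;
- TB suspects reused as controls enter these comparisons only if they are ART-naive.

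**In section 1d,** keep the fatal-versus-survivor comparison in all 290 patients, adjusted or stratified by ART status at enrolment. Use the ART-naive subset as a sensitivity analysis for the question about the state before ART.

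**Cost.** No new patients or samples are needed, and the activity schedule already presupposes that ART status at recruitment is known. Precision against controls falls slightly, by the amounts in step 6. The PLEX-ID contrast with controls would have fewer than 90 fatal cases, and the text should say so.
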